6.4.5. Microbiome analysis

Further characterization of *H. influenzae*, *M. catarrhalis* and HRV strains will be performed. Details of the statistical analyses will be released in a separate additional analysis request.

CONFIDENTIAL201112 (EPI-NTHI-001 BOD APA)
Statistical Analysis Plan Amendment 2 Final**6.4.6. Biomarkers**

Descriptive statistics (N, mean, median, SD, minimum, maximum, first and third quartiles) for the level of each quantitative biomarker/haematology parameter will be tabulated for visit 1 and visit 3. The difference in sample mean will be reported together with a confidence interval.

Number and percentage of patients with fibrinogen, human serum C reactive protein (hsPCT), C-X-C Motif Chemokine Ligand 10 (CXCL10) values outside the laboratory normal ranges will be tabulated for visit 1 and visit 3.

Descriptive statistics will be presented overall and by GOLD grade at enrolment.

Changes in biomarkers will be evaluated according to the number of exacerbations occurred in the observation period using Pearson's correlation coefficient (or Spearman's rank-order correlation coefficient if the normal distribution assumption is not met).

The mean number of exacerbations per year overall, by severity of exacerbation and by presence of Hi and Mcat in the sputum collected at exacerbation visits will be calculated for patients with blood eosinophil levels $\geq 2\%$ and for those with blood eosinophil levels $< 2\%$ (the level measured for each patient at visit 1 will be used for this categorization).

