identified by clinical examination and/or corroborative testing. The worsening in respiratory symptoms may or may not warrant a change in underlying therapy and the symptoms will typically resolve over a period of days to weeks" [ERS/ATS Draft Task Force Recommendations, Major Symposium, ERS Scientific Congress Barcelona 2013]. AECOPD are often associated with concurrent deteriorations in pulmonary function and increases in both local and systemic inflammation. Higher exacerbation rates have been related to a faster decline in lung function and are known to have a negative effect on the patient's quality of life. Moreover, frequent exacerbations are associated with significant mortality, particularly if they require hospitalisation. Between 40 - 60% of medical expenditure for COPD is a direct consequence of AECOPD [Cazzola, 2008]. The severity of AECOPD can be graded according to the intensity of medical intervention required (see [Table 2](#)) [Wedzicha, 2007].

Table 2 Classification of severity of AECOPD

Grade	Intensity of medical intervention
Mild	Controlled with an increase in dosage of regular medications
Moderate	Requires treatment with systemic corticosteroids and/ or antibiotics
Severe	Requires hospitalisation

Bacteria, viruses and environmental pollution are also thought to be important causes of AECOPD [[Sapey](#), 2006]:

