4.2. Inclusion criteria for enrolment

Deviations from inclusion criteria are not allowed because they can potentially jeopardise the scientific integrity of the study and regulatory acceptability of the study or subject safety. Therefore, adherence to the criteria as specified in the protocol is essential.

All subjects must satisfy ALL the following criteria at study entry:

- Subjects who, in the opinion of the investigator, can and will comply with the requirements of the protocol (e.g., completion of electronic Diary Card, sputum sampling, pre- and post-bronchodilator spirometry, return for follow-up visits).
- Written informed consent obtained from the subject.
- Male or female aged 40 years or older at the time of enrolment.
- Confirmed diagnosis of moderate to very severe COPD based on post-bronchodilator spirometry (i.e. forced expiratory volume in 1 second [FEV₁] over forced vital capacity [FVC] ratio [FEV₁/FVC] < 0.7 and FEV₁ < 80% predicted [GOLD grades 2, 3 and 4]).
- Stable COPD patient* with documented history** (e.g. medical record verification) of at least 1 moderate or severe AECOPD within the 12 months before study entry.

** Patient for whom the last episode of AECOPD is resolved for at least 30 days at the time of study entry.*

***Note: A documented history of a COPD exacerbation (e.g., medical record verification) is a medical record of worsening COPD symptoms that required systemic/oral corticosteroids and/or antibiotics (for a moderate exacerbation) or*

hospitalization (for a severe exacerbation). Prior use of antibiotics alone does not qualify as an exacerbation history unless the use was associated with treatment of worsening symptoms of COPD, such as increased dyspnea, sputum volume, or sputum purulence (color). Subject verbal reports are not acceptable.

Refer to the SPM for details on what is accepted as documented history of AECOPD. Refer to [Table 2](#) for the definitions of moderate and severe AECOPD.

- Current or former tobacco smoker (cigarette) with a smoking history of ≥ 10 pack-years OR a subject exposed to biomass smoke for ≥ 20 years [[Guoping Hu, 2010](#)]

Refer to the [glossary of terms](#) for the definitions of pack-years, current and former smoker.

- Able to provide a sputum sample at Screening Visit.

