6.3. Outline of study procedures

Table 4 presents the study procedures involved during scheduled [stable] visits.

Table 4 List of study procedures for scheduled visits

Epoch	Epoch 001			
	Type of contact	Screening Visit	Visit 1	Visit 2
Time point	Pre-Month 0	Month 0	Month 6	Month 12
Informed consent ^a	●			
Check inclusion/exclusion criteria ^a	●	○		
Record demographic data ^a	●			
Record medical history	●			
Record history of AE COPD within the previous year ^b	●			
Record intercurrent comorbidities ^c	○	●	●	●
Record history of pneumococcal and influenza vaccination	○	●	●	●
Smoking exposure history (ATS-DLD-78A questionnaire)/biomass exposure history (Biomass Exposure questionnaire)	○			
Smoking status	●	●	●	●
Physical examination including vital signs ^h	●	○	○	○
Urine Pregnancy Test	●	●	●	●
Measure/ record height and weight ^d	●			●
Pre- and post-bronchodilator spirometry ^e	●			●
Chest X-ray ^f	●			
Record subject's COPD status (stable, recovered or not recovered)		●	●	●
Record current medication		●	●	●
Record healthcare resource utilisation		●	●	●
Record additional treatments prescribed by primary and secondary care physicians		●	●	●
Train subject on use of electronic Diary Card and assign electronic Diary Card to the subject	○	○		
Return electronic Diary Card				○
Sputum sampling ^g	●	●	●	●

Epoch	Epoch 001			
Type of contact	Screening Visit	Visit 1	Visit 2	Visit 3
Time point	Pre-Month 0	Month 0	Month 6	Month 12
Blood samples for biomarkers		●		●
Record Adverse Events (AEs)* ^a	●	●	●	●
Record serious adverse events (SAEs) ^a	●	●	●	●
Screening conclusion	●			
Study conclusion				●
HRQOL questionnaires:				
CAT		0	0	0
SGRQ-C		0	0	0

● is used to indicate a study procedure that requires documentation in the individual eCRF.

0 is used to indicate a study procedure that does not require documentation in the individual eCRF.

^a For non-eligible subjects, only informed consent, inclusion/ exclusion criteria, demographic data and SAEs related to study participation that occurred after signing the informed consent pages need to be completed in the subject's eCRF. For other activities, 'not done' can be indicated.

^b Record both documented and self-reported, non-documented AECOPD. Subjects need documentation for at least 1 moderate or severe AECOPD within the previous year to be eligible for study participation.

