6.4. Analysis of tertiary objective

The analyses of the tertiary objectives will be performed on the full analysis set.

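### SAP 6.4.6 sets no stability or timing condition on Visit 3 blood, so the correlation of biomarker change with exacerbation count can be biased upward

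*SAP*

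**What the plan says.** Blood for hsCRP, fibrinogen, CXCL10 and haematology is taken only at Visit 1 and Visit 3 (Protocol 6.4.2.16 and Table 4). SAP 6.4.6 says that the results "will be tabulated for visit 1 and visit 3", that "The difference in sample mean will be reported together with a confidence interval", and that "Changes in biomarkers will be evaluated according to the number of exacerbations occurred in the observation period". The statistic is Pearson's coefficient, or Spearman's if normality fails, with no covariate. On the population, SAP 6.4 says "The analyses of the tertiary objectives will be performed on the full analysis set".

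SAP 6.4.6 mentions neither COPD status nor time since the last AECOPD, and none of the elimination codes in SAP 5.4.4 names a Visit 3 at which the patient had not recovered. Such visits are foreseen. Table 4 of the protocol has sites "Record subject's COPD status (stable, recovered or not recovered") at Visits 1 to 3, and SAP 6.3.5 tabulates how often each status occurs.

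For Visit 1, Protocol 4.2 defines a stable patient as "Patient for whom the last episode of AECOPD is resolved for at least 30 days at the time of study entry", and Protocol 6.4.2.1 has the criteria checked again at Visit 1. No such interval is set for Visit 3.

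**The concern.** The protocol's own background says that "AECOPD are often associated with concurrent deteriorations in pulmonary function and increases in both local and systemic inflammation". A blood sample taken in or soon after an AECOPD may therefore read high for a while. The more AECOPD a patient has in the year, the more likely one of them falls shortly before Visit 3. Exacerbation count and timing of the second sample are then linked, and only the first sample is protected.

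This is the only planned analysis that relates exacerbation count to change in a biomarker. If a temporary rise near the last event feeds into it, a positive correlation could be read as a lasting inflammatory effect of exacerbations when none exists. For an analysis meant to generate hypotheses, the harm is a false lead.

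**Working it through.** **Step 1. Conditions at each sample.**

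| | Visit 1 | Visit 3 |
|---|---|---|
| Minimum time since AECOPD resolved | 30 days (Protocol 4.2) | none |
| Antibiotic-free period | 1 month (Protocol 4.3) | none |
| AECOPD at the planned date | not eligible yet | handled as an AECOPD visit; stable visit moved if that can be done (Protocol 3.1.1, Table 6 footnote) |
| Status condition in SAP 6.4.6 | none | none |

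Elsewhere the SAP does use a stability condition: for the sputum proportions (SAP 6.2, with a definition of a confirmed stable visit), for CAT and SGRQ-C (SAP 6.3.6) and for EXACT scores at scheduled visits (SAP 6.4.1).

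Table 6 allows 175 to 203 days between Visits 2 and 3, with 182 optimal. A visit due on the optimal day can move 203 − 182 = 21 days within the window, which is shorter than the 30 days required before Visit 1.

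**Step 2. Planning figures.** The documents give no figure for the biomarker correlation. The sample size it would use can be checked: 200 × 0.80 = 160 completers (Protocol 9.2). Table 13 at 1 AECOPD per subject-year is 1 ± 1.96 × √(Φ/160), which gives 0.85–1.15, 0.81–1.19 and 0.78–1.22 for Φ = 1, 1.5 and 2, as printed.

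**Step 3. How often Visit 3 follows an AECOPD.** With onsets spread evenly over the year (assumption), the share of patients with an onset in the last d days is 1 − exp(−rate × d/365).

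| Rate per year (Table 13) | d = 14 | d = 30 |
|---|---|---|
| 1 | 3.8% | 7.9% |
| 2 | 7.4% | 15.2% |
| 3 | 10.9% | 21.9% |

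By patient, the chance of at least one of n events in a 30-day window is 1 − (1 − 30/365)^n: about 8%, 16% and 29% for n = 1, 2 and 4, and 0 for n = 0. That gradient is the source of the bias.

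**Step 4. Correlation induced with no lasting effect.** Simulation with 160 patients, 200 runs per scenario, rates of 1, 2 and 3 per year and Φ = 1.5 from Table 13. Change score = noise (SD 1) + temporary rise. Assumptions not in the documents: AECOPD lasts 14 days; rise of 1 or 2 SD of the change score; after recovery the rise either ends at once or decays with a half-life of 7 or 14 days. Simulation error on a mean r is about (1/√160)/√200 = 0.006.

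| Handling of Visit 3 | Mean Pearson r, rise ends at recovery | Mean Pearson r, half-life 7–14 days |
|---|---|---|
| Held on schedule whatever the status | 0.04 to 0.11 | 0.07 to 0.23 |
| Moved to the day of recovery | about 0 | 0.07 to 0.22 |

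With no acute rise, r is about 0. In the second row with a half-life, the 95% CI for r lies wholly above 0 in 14% to 79% of runs, against a nominal 2.5%.

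**Step 5. With a 30-day interval after recovery at Visit 3.** Mean r is −0.01 to 0.05 in every scenario, and the CI lies wholly above 0 in 1% to 7% of runs. About 89%, 79% and 71% of patients remain at 1, 2 and 3 AECOPD per year.

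**The case against.** The strongest reply is the conduct rule. An AECOPD at the time of a scheduled visit becomes an AECOPD visit, Table 5 lists no blood sample there, and the stable visit waits until the patient is stable again. Visit 3 may even exceptionally fall outside its window. SAP 6.2 repeats the re-scheduling rule. A reader of SAP 6.4.6 alone might infer that Visit 3 blood is drawn whatever the patient's condition; the protocol does not support that. Counting active days as well (14 + 30 = 44 days) gives 12%, 23% and 40% for 1, 2 and 4 events, but re-scheduling is meant to remove the active part.

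The size also rests on outside assumptions. With visits falling during an AECOPD moved to 7 days after recovery, a 1 SD rise and more dispersed counts (negative binomial, dispersion 1), the Spearman correlation at 1 and 2 events per year is only 0.05 and 0.07 with a 7-day half-life, and 0.02 and 0.03 with a 3-day half-life.

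Finally, the biomarker objective is tertiary and concerns specimen collection, no biomarker endpoint is listed (Protocol 9.1.3, SAP 4.3), and SAP 7 limits every analysis to supportive or hypothesis-generating use.

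All of this narrows the point without removing it. Re-scheduling is conditional and sets no interval after recovery. The second row of the Step 4 table shows that, for a marker that falls slowly, perfect re-scheduling leaves most of the bias in place.

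**Conclusion.** The gap is real and modest in importance. The plan protects the first blood sample from a recent AECOPD and not the second, then correlates the difference with the number of AECOPD. For markers that rise in an AECOPD and return slowly, for which hsCRP and fibrinogen are the natural candidates, the coefficient can be biased upward. The expected r with no lasting effect runs from about 0 to 0.23 across the assumptions in Step 4.

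A reader might infer that the correlation will be positive regardless. That is too strong: if the marker returns to baseline at recovery and re-scheduling always works, the bias is about 0. Nor do the documents give a direction for every haematology parameter in SAP 6.4.6.

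A reader might also take the difference in sample means as an unpaired comparison that mixes in dropouts. The text does not say so. SAP 5.3 lets each analysis follow the patients evaluable for it, and among patients with both values the difference in means equals the mean within-patient change. This is an ambiguity of wording only.

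**What to change.** In SAP 6.4.6:

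- Base the Visit 1 to Visit 3 biomarker change, and its correlation with exacerbation count, on Visit 3 samples from confirmed stable visits as defined in SAP 6.2.
- Add a sensitivity analysis limited to patients with no AECOPD or at least 30 days since the end of the last one, or adjusted for time since the last AECOPD with a separate category for patients who had none. This step is needed as well: in the scenario where every visit waits for recovery, all Visit 3 samples are already stable and r is still 0.07 to 0.22 with a 7–14 day half-life.
- Tabulate days since the last AECOPD at Visit 3, and show the result in all patients for comparison.
- As a clarification, state that the mean difference is the within-patient change in patients with both values.

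The cost is SAP wording. COPD status and AECOPD end dates are already in the eCRF (Protocol 6.4.2.9 and 3.1.1.1), though a rule is needed for missing end dates. The 30-day analysis keeps about 71% to 89% of patients under the assumptions above and loses frequent exacerbators disproportionately, which is a reason to show it beside the other results and not alone.

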6.5. Analysis of safety

The analysis of serious adverse events will be performed on the full analysis set.

Adverse events (AEs) and serious adverse events (SAEs) considered possibly related to the study participation and patients withdrawal due to AEs and SAEs during the entire study period will be described in detail.

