5.2. All enrolled set

The all enrolled set will include patients from the all screened set minus those that were screening failures.

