5.3. Full Analysis Set

The Full Analysis Set (FAS) will include patients from the all enrolled set except for those who discontinued the study at Visit 1.

Study objectives will be assessed on the FAS. The population set for each analysis will change according to the subjects evaluable for the specific endpoint.

5.3.1. Change in analysis population from protocol amendment 2

The analysis population is aligned with protocol amendment 2.

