5.4.2. Elimination from All Enrolled Set

Code 800 (fraudulent data), code 900 (invalid informed consent) and code 2010 (Protocol violation - inclusion/exclusion criteria) will be used for identifying patients eliminated from All Enrolled Set.

CONFIDENTIAL

201112 (EPI-NTHI-001 BOD APA)
 Statistical Analysis Plan Amendment 2 Final

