5.4.3. Elimination from the Full Analysis Sets (FAS)

Code 800 (fraudulent data), code 900 (invalid informed consent) and code 2010 (Protocol violation - inclusion/exclusion criteria) will be used for identifying patients eliminated from FAS.

Of note, the only difference between the All Enrolled Set and the FAS comes from patients that withdraw from the study at visit 1. These patients will be in the All Enrolled Set but will not be in the FAS. However, this is not a protocol deviation and is not mentioned in this section.

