5.4.4. Elimination codes details

A list of reasons for elimination from the analyses (interim analysis and final analysis), is reported below:

Code	Condition under which the code is used
800	Fraudulent data
900	
 1. Informed consent deviations 
 1.a. Signed informed consent not available on site 1.b. Wrong informed consent version signed 1.c. Informed consent not signed and/or dated by subject 1.d. Informed consent not signed and/or dated by appropriated site staff 1.e. Informed consent not signed prior to any study procedure 1.f. Other informed consent deviations 2. Eligibility deviations 
 2.a. Biological sample specimen procedures 
 2.a.a. PII recorded in label of sample
2010	
 1. Eligibility criteria not met
2040	
 1. Excluded medication, vaccine, or device 
 1.a. Prohibited medication as per protocol (e.g., antibiotics administration will impact the primary endpoint)

CONFIDENTIAL201112 (EPI-NTHI-001 BOD APA)
Statistical Analysis Plan Amendment 2 Final

Code	Condition under which the code is used
2050	
 1. Not withdrawn after developing withdrawal criteria 
 1.a. Not withdrawn after developing withdrawal criteria other than prohibited vaccination/medication
2090	
 1. Assessment or time point completion 
 1.a. Out of window visit (assessment) for efficacy 
 1.a.a. Sputum sample collection outside the 96 hour-interval since exacerbation onset
2100	
 1. Study procedures 
 1.a. Biological sample specimen procedures 
 1.a.a. Low volume (not sufficient to perform testing) 1.a.b. Mislabeled (sample not tested)
2110	
 1. Study procedures 
 1.a. Biological sample specimen procedures 
 1.a.a. Incorrect or expired sample tube used 1.a.b. Incorrect spinning/processing of sample

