6.1. Analysis of demographics/baseline characteristics

The analysis of demographic/baseline characteristics will be performed on the FAS and on the all enrolled set only if the percentage of enrolled patients excluded from the FAS is 5% or more.

The following characteristics at enrolment will be summarized using descriptive statistics:

- Demographics such as age at enrolment, sex and race.
- Present and past medical history.
- History of AECOPD within the previous year (overall and by AECOPD severity).
- Pre- and post-bronchodilator spirometry results.
- COPD status using the GOLD grade.
- Smoking/biomass exposure history status.
- Selected results and several risk factors from the ATS-DLD-78-A questionnaire.
- Physical examination/vital signs results such as height, weight, BMI, heart rate, respiratory rate, systolic and diastolic blood pressure.
- Chest X-rays results.
- Intercurrent comorbidities (reported at visit 1)
- History of pneumococcal and influenza vaccination (reported at visit 1)

CONFIDENTIAL

201112 (EPI-NTHI-001 BOD APA)
 Statistical Analysis Plan Amendment 2 Final

The following descriptive statistics will be adopted:

- The frequency and the percentage of each category will be reported for categorical variable.
- Number of non-missing observations, mean, median, standard deviation, minimum and maximum will be provided for quantitative variable.

All tables will be also generated by country.

Demographics and baseline characteristics will be also summarized for study sample for interim analysis.

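### SAP 6.5 analyses SAEs on the FAS, so procedure-related SAEs that the protocol collects in screening failures and Visit 1 discontinuations can be left out of the SAE count

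*SAP*

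**What the plan says.** SAP 6.5 has two sentences. The first names a population: "The analysis of serious adverse events will be performed on the full analysis set". The second promises a detailed description of adverse events and, in the same terms, of "serious adverse events (SAEs) considered possibly related to the study participation and patients withdrawal due to AEs and SAEs during the entire study period". It sets the period but not the analysis set.

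The sets are nested. SAP 5.2: "The all enrolled set will include patients from the all screened set minus those that were screening failures". SAP 5.3: "The Full Analysis Set (FAS) will include patients from the all enrolled set except for those who discontinued the study at Visit 1". SAP 5.4.3 confirms this for patients who withdraw at Visit 1: "These patients will be in the All Enrolled Set but will not be in the FAS". Section 5.4.3 also removes codes 800 (fraudulent data), 900 (consent deviations) and 2010 from the FAS. SAP 5.4.4 describes code 2010 as "Eligibility criteria not met".

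On the collection side, protocol 7.2.1 has SAEs related to study participation recorded from consent until discharge from the study. Footnote a of protocol Table 4 requires these SAEs in the eCRF of non-eligible subjects as well.

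**The concern.** The study gives no product, so its safety question is harm from study procedures. Some of those procedures come before a subject can belong to the FAS: spirometry (protocol 6.4.1.11) and spontaneous or induced sputum sampling (6.4.1.14) are done at screening, and sputum and blood are taken at Visit 1 (Table 4). Being able to give a sputum sample at screening is also an inclusion criterion (protocol 4.2). A subject whose sampling is stopped by a reaction can thus become a screening failure because of that reaction, and a subject who has an event at Visit 1 can withdraw there because of it. Either way the event itself takes the subject out of the set on which SAEs are analysed.

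At stake is the completeness of the safety account in the study report. The primary and secondary estimates are not affected.

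**Working it through.** No arithmetic applies, because the documents give no number of screening failures, Visit 1 discontinuations or SAEs. The check compares the set definitions with the collection rules.

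**1. Who is outside the FAS.** The All Screened Set (SAP 5.1) holds consented patients evaluated for enrolment, without those who have invalid consent or fraudulent data (codes 900 and 800). From the definitions above:

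FAS = All Screened Set − screening failures − code 2010 patients − Visit 1 discontinuations

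Code 2010 "will be used for identifying patients eliminated from All Enrolled Set" too, and its meaning is an eligibility failure. It may overlap with screening failures, and the SAP does not settle whether it is a separate group.

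**2. Whose SAEs are collected, and which reach the analysis in the first sentence of 6.5.**

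| Subject with a related SAE | Collected under the protocol? | In the FAS? | In the FAS-based SAE analysis? |
|---|---|---|---|
| Event at screening, then screening failure | Yes (7.2.1; Table 4 footnote a) | No (SAP 5.2) | No |
| Event at screening or Visit 1, discontinues at Visit 1 | Yes (7.2.1) | No (SAP 5.3, 5.4.3) | No |
| Event at screening, stays in the study, no elimination code | Yes (7.2.1) | Yes | Yes |

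The first two rows are the gap. The third shows that the screening period as such is not lost; the gap concerns only patients outside the FAS.

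**3. Direction.** The FAS is a subset of the All Screened Set, so a count of SAEs on the FAS can be lower than the count on the wider set but never higher. This does not carry over to percentages. Let the FAS have x events-bearing subjects out of n, and the omitted group y out of m. The percentage on the wider set, (x + y)/(n + m), exceeds x/n only if y/m > x/n. The documents give none of these numbers, so the direction for a percentage is open.

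**4. Does the second sentence of 6.5 close the gap?** If the FAS carries over from the first sentence, early leavers are missed there too. If it does not, the sentence may cover them, but the population is unstated.

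**5. Do other outputs close it?** SAP section 6 tabulates screening failures by reason, patients who withdrew at Visit 1, and withdrawals by reason and visit. Protocol 8.2 lists SAE and non-serious AE among the recorded withdrawal reasons. These give counts by reason, not descriptions of events. SAP section 10 mentions an SAE listing, but the mock tables are in a separate document (SAP section 13), so its population cannot be checked here.

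**6. Does the protocol require the FAS for safety?** Protocol 9.3.3 ties the FAS to the study objectives. Safety is not among the objectives in protocol section 2, and protocol 9.3 to 9.8 names no set for safety. A wider set would not contradict the protocol.

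**The case against.** The strongest defence is that the second sentence of 6.5 already does the job. The protocol collects only AEs and SAEs that are related to study participation or lead to withdrawal, and that sentence promises both classes for the whole study with no restriction to a set. On that reading nothing collected goes undescribed. This reading is possible and may be what was intended. It does not settle the matter, because the FAS is the only set named in 6.5 and the opposite reading is equally open.

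A second defence is that a Visit 1 exit caused by an AE would show in the withdrawal tables. That stands as mitigation for enrolled patients, but a count under a reason code is not the description that 6.5 promises.

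Third, the consequence is small: there is no study product, safety is not an objective, and all analyses are descriptive (SAP section 7). Collection and 24-hour reporting (protocol 7.2.1, 7.3.1) do not depend on an analysis set. All of this stands and limits the weight of the point.

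Three stronger readings that a reader might infer are not supported:

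- **That SAEs will be omitted from the report.** The documents show only that the rule as written can omit them.
- **That the protocol expects SAEs from sputum sampling at screening.** Section 6.4.1.14 is a precaution: a subject judged at risk is not sampled and not included.
- **That the 5% rule in SAP 6.1 gives a size.** That section repeats the demographic tables "on the all enrolled set only if the percentage of enrolled patients excluded from the FAS is 5% or more". The threshold counts patients, leaves out screening failures and says nothing about SAEs.

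**Conclusion.** The point holds as a gap in SAP 6.5. The only population it names for safety is narrower than the group in which the protocol collects related SAEs, and leaving that population can be a consequence of the event. A FAS-based SAE count can be too low and cannot be too high; nothing similar can be said of a percentage. The second sentence of 6.5 and the withdrawal tables soften the gap without closing it.

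The number of affected events cannot be derived and may be zero. The conclusion rests on reading the first sentence of 6.5 literally and on the set definitions in SAP 5.1 to 5.4. It would change only if the separate table and listing shells define a wider safety population, which cannot be seen from these documents. The matter is one of complete safety reporting and should be corrected because correction costs so little.

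**What to change.** In SAP 6.5, replace the FAS with the existing All Screened Set (SAP 5.1) and apply it to both sentences. That set rests on signed consent and so matches the start of SAE collection; no new analysis set is needed. In the SAE listing, flag each subject as a screening failure, another patient outside the FAS, or in the FAS.

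Codes 800 and 900 also remove patients from the All Screened Set (SAP 5.4.1). Code 900 is broad and covers, for example, an undated consent form, so such patients may have undergone study procedures. List separately any related SAE in a code 900 patient where use of the data is permitted.

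The cost is a rewording of two sentences, one flag and a matching edit to the listing shell. Related SAEs in non-eligible subjects are already required in the eCRF, so no new data are collected. There are two small downsides. In non-eligible subjects only related SAEs are required, so non-serious AEs there may be incomplete and the report should say so. Any percentage also needs its denominator stated, because early leavers had little exposure to study procedures.
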